[name]

Study Protocol with Statistical Analysis Plan (SAP)

Official Title of the Study: Knowledge Accessibility and Availability in Forming
Knowledge-to-Text Inferences among Middle Grade Readers

NCT number: NCT03782012

Date of the Document: 29 August 2023

SCIENTIFIC BACKGROUND:

All major theories of reading comprehension (e.g., Kintsch, 1998; van den Broek et al., 1996) emphasize the importance of inferencing. Recent adolescent-based research shows that inferencing improves across grades 6-12, uniquely accounts for variance in sentence- and passage-level comprehension, and that individual differences in inferencing relate in a principled way to variations in reading comprehension for readers of all abilities (Barth et al., 2015_b; Barnes et al., 2015). These findings suggest that comprehension requires inferencing and that comprehension fails when readers do not possess relevant knowledge (i.e., availability) or are slow in their retrieval (i.e., accessibility) and integration of knowledge from text or semantic memory during reading (Kendeou, 2015). To date, only one study has examined the effects of knowledge availability and accessibility on inferencing among adolescents. Those results reveal that students will twice as likely use easily accessible knowledge to form inferences than knowledge that takes longer to retrieve (Barnes et al., 1996). But this study did not measure speed of forming inferences, used first grade texts, and excluded less skilled middle grade readers. From the cognitive science literature, few studies have examined the effect of retrieval practice on knowledge availability and inferencing (Butler, 2010; Karpicke & Blunt, 2011; Smith & Karpicke, 2014). Results show that retrieval practice enhances knowledge availability for text content and leads to improved inferencing on near and far transfer tasks. However, these studies – conducted on adult readers – did not measure knowledge accessibility or individual difference factors.

OBJECTIVES:

To extend this limited body of research, this project conducts experimental studies with three objectives:

- (1) To conduct experimental studies to determine the extent to which variations in knowledge base availability and accessibility influence the rate and accuracy of forming inferences.
- (2) To investigate whether individual difference factors are potential sources of variability in explaining inferencing and reading comprehension.

Method. Participants will complete a four-phase experiment. Procedures represent a modification of those used by Barnes et al. (1996). In Phase 1, students learn a knowledge-base of 18 facts about a pretend planet named Gan. In Phase 2, which occurs after students learn the knowledge base to criterion (perfect recall), students will read and listen to a six-episode text. Immediately after hearing each text section, the computer asks students questions measuring understanding (i.e., literal, coherence inference, and elaborative inference questions). Phase 3 occurs immediately after hearing all text sections and retests retention of the knowledge-base and inference making. One week later, Phase 4 retests the knowledge-base and inference making. Students also take a larger test battery.

Phase 1: The Knowledge Base. The knowledge base comprises 18 details that relate to the text. Each detail will appear on the computer screen in a block at a rate of 1 item every five seconds. Participants will initiate the presentation of the first detail by pressing the space bar. For each detail, the computer will display the fact in the middle of the tenth row of the monitor; E-Prime (Schneider et al., 2002) will also read the detail to the student. An Immediate Recall Task and a Verbal Recall Task will assess knowledge base acquisition to provide an indication of how easily the students acquired the knowledge-base and will serve to teach the knowledge-base to criterion, as follows.

Immediate Recall. The computer will ask the participant to recall as many details as he or she can with no time restriction on recall. We will index accessibility by the amount of time taken to recall the knowledge-base and availability by the total number of knowledge-base details correctly recalled.

Verbal-Recall Task. Next, the computer will ask each participant 18 questions to assess his or her literal memory for each knowledge-based item, with each question read and presented in middle of the tenth row of the monitor. After completing all 18 questions, the computer will provide the correct answer for each question with only items that the student recalls incorrectly

presented more than once. Presentation will stop when the participant answers all questions correctly. The computer will time responses to questions from the offset of the question to the onset of the response to provide a measure of accessibility of each knowledge-base item.

Phase 2: Text and Questions. After the Verbal-Recall Task, the computer will present the six-section text, one section at a time. Seven questions asked immediately after each text section assess various aspects of text comprehension (literal questions, coherence inference questions, and elaborative inference questions). The computer will time responses to questions from the offset of the question to the onset of the response to provide a measure of accessibility of each item. When a student answers a question incorrectly or incompletely, the research assistant will use a nonspecific prompt to elicit a fuller response (i.e., tell me more about that).

Phase 3: Retention of the Knowledge Base. After the student completes all text sections and questions, the computer will test memory for the knowledge-base using the Immediate Recall Task and Verbal Recall Task described for Phase 1 with no feedback provided.

Phase 4: Long-Term Retention of the Knowledge Base. One week later, students' retention of the knowledge-base will be tested using the Immediate Recall Task and Verbal Recall Task described for Phase 1. We will also administer additional measures to assess reading comprehension, inferencing, and individual difference factors.

Assessments. Assessments measure the constructs of reading comprehension, inferencing, word reading efficiency, metacognition, working memory, and background knowledge.

Statistical Analysis Plan for Study 1.

Data Analysis. We will screen for missing data and outliers and evaluate the distributional properties of observed variables, making transformations as necessary and appropriate. If possible, we will correlate non-plausible values or list them as missing if not possible, and label extreme data points.

Analytic Approach. We will model the effects of knowledge availability and accessibility on inferencing without dichotomizing the distribution of comprehension. To determine whether reader characteristics (i.e., knowledge availability and accessibility, metacognition, reading comprehension, word reading efficiency, background knowledge, working memory, and grade) make unique contributions to inferencing, we will fit mixed effects explanatory item response models to the trial-by-trial inferencing accuracy and speed data using SAS PROC MIXED with item-level accuracy and reading speeds cross classified between person and items. We will also nest people within grade, treating grouping variable for people such as grade and items as fixed factors. If limited variability exists in the accuracy data, we will only model response time data. The sampling plan maximizes power to detect whether variations in knowledge accessibility and availability relate to differences in their rate and accuracy in which students use that knowledge to form inferences. The study has sufficient power to test secondary hypotheses which will examine if accessibility of knowledge affects inferencing with that knowledge more so for less skilled than for skilled comprehenders after controlling for knowledge availability and whether individual difference factors such as working memory, metacognition, and reading fluency relate to differences in the accuracy and rate of forming knowledge-based inferences and comprehension of text.

Study 2:

Scientific Premise. In the transfer literature, some evidence suggests that conditions of initial learning improve the direction and magnitude of transfer. For example, several studies show that the greater the degree of initial learning, the higher the probability of positive transfer (e.g., Bruce, 1933; see Ellis, 1965) as does increasing the quantity and variability of training question types or problems (see Kimball & Holyoak, 2000). These findings suggest that if a student receives multiple opportunities and ways to access information in memory, it increases retention of the information and accessibility to the information which can improve use of that knowledge on related tasks. To date, no study has evaluated how initial learning conditions designed to enhance knowledge availability and accessibility effect knowledge-based inferencing and comprehension among middle grade less skilled readers.

Participants. Study participants (n = 180) will come from Storm Lake Community School District students in grades 5-8. We anticipate that students will come from diverse socio-economic and ethnic backgrounds.

Power and Design. We estimate the sample associated with an effect size of 0.25, alpha 0.05, and with over 80% power at 136 participants for between group differences, 36 for within group differences, and 180 for the interaction. Randomization will occur within grade, with all qualified students in grade 5 available for randomization because they did not participate in Study 1.

Procedure. Study 2 follows the same procedure as Study 1 with the following changes. After the Verbal-Recall Task, the computer will present the six-section informational text one section at a time with each section approximately 500 words in length. Immediately after studying, the computer reassesses the students' retention of the knowledge base with the Immediate Recall Task and Verbal Recall Task. Next, students will reread two of the text sections (reread passages condition), repeatedly take the same test on another two text sections (same test) and repeatedly take different tests on the other two text sections (variable text). Immediately following, students' retention of the knowledge-base will be reassessed with the Immediate Recall and Verbal Recall Tasks.

Assessments. One week later, participants will return to assess their knowledge base retention and inferencing and comprehension of the passages. Study 1 assessments will also be administered.

Statistical Analysis Plan for Study 2.

Data analysis. We will screen for missing data and outliers and evaluate the distributional properties of observed variables, making transformations as necessary and appropriate. When possible, we will correct non-plausible values or list them as missing if we cannot correct them and label them extreme data points.

Analytic approach. Data analysis will use repeated measures analysis of variance models to examine the effect of the experimental condition on knowledge retention. Separate ANOVAS will analyze scores obtained on the question types and the efferent error types by condition. The sampling plan maximizes power to examine Aim 2. The analyses include factors such as socioeconomic, gender, and disability status to determine whether these demographic factors impact inferencing.

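### Study 1's model reads as a between-student test of accessibility and gives the recorded fact-level latencies no role

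*Combined protocol and SAP*

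**What the plan says.** - **Level of the predictor.** The Analytic Approach for Study 1 asks whether "reader characteristics (i.e., knowledge availability and accessibility, metacognition, reading comprehension" and four further entries, from word reading efficiency to grade, each contribute uniquely to inferencing. The other entries in that list describe the student.
- **Index of accessibility.** Under Immediate Recall: "We will index accessibility by the amount of time taken to recall the knowledge-base". That gives one value per student at each administration.
- **A second, finer measure.** In Phase 1, "students learn a knowledge-base of 18 facts about a pretend planet named Gan". The Verbal-Recall Task times the answer to each fact question "to provide a measure of accessibility of each knowledge-base item".
- **Outcome.** The Analytic Approach states that "we will fit mixed effects explanatory item response models to the trial-by-trial inferencing accuracy and speed data", with persons crossed with items.
- **Question posed.** The Scientific Background reports from the study being extended that "students will twice as likely use easily accessible knowledge to form inferences than knowledge that takes longer to retrieve". Aim 1 and the secondary hypothesis refer to inferences drawn from the same knowledge whose accessibility is measured. Objective 1 uses causal wording.

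The analysis section does not say that fact-level latency enters the model, which inference question depends on which fact, or whether within-student and between-student effects are to be separated.

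**The concern.** Two questions are possible. One is whether students who retrieve quickly on average infer better or faster. The other is whether, for a given student, a fact retrieved quickly is used more often or sooner than a fact retrieved slowly. The motivating result is phrased in the second form; the model as written reads as the first.

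The difference affects interpretation. A student-level coefficient can carry any stable trait that is related to both recall speed and inferencing and is not captured by the planned covariates. Comparing a student's faster facts with the same student's slower facts removes all stable traits. The risk is sharper for the rate outcome, because recall latency and inference response time are timed in the same way, from the end of the question to the start of the answer. A generally quick responder is therefore quick on both. If accuracy shows little variability, the plan models response time alone.

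**Working it through.** The plan gives no figure for this point. Its only Study 1 power statement concerns correlations among constructs and latent regressions, and nothing here rests on it.

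**1. Data available.** Inputs are 300 students (the headline sample size; the same sentence also gives 160 per grade, which is not used here), 18 facts and six text sections. "Seven questions asked immediately after each text section assess various aspects of text comprehension".
- Fact latencies per administration: 300 × 18 = 5,400.
- Phase 2 question trials: 7 × 6 = 42 per student, and 300 × 42 = 12,600. The questions are of mixed type and no map to facts is given.
- Independent values of a student-level predictor: 300. Trial-level outcomes do not raise that number, and a random student intercept does not remove confounding of a student-level predictor.

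**2. Why the student-level slope is biased.** Let L be fact latency, U an unmeasured trait, β the true fact-level slope and γ the trait's effect on a continuous outcome. Then

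E(slope on student mean) = β + γ × Cov(mean L, U) / Var(mean L).

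Illustrative assumptions: total latency variance 1, of which 0.30 lies between students, 0.20 between facts (common to all students) and 0.50 is residual; the student component of latency correlates √0.50 = 0.71 with U.
- Cov(mean L, U) = √0.30 × √0.50 = 0.387
- Var(mean L) = 0.30 + 0.50/18 = 0.328
- Ratio = 0.387/0.328 = 1.18

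With β = 0 the expected slopes are 0.118, 0.236 and 0.354 for γ = 0.1, 0.2 and 0.3. A simulation of 500 replicates (residual SD 1, student and item SD 0.4) gave:

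| β | γ | Student-level slope (rejects) | Within-student slope (rejects) |
|---|---|---|---|
| 0 | 0 | 0.00 (6%) | 0.00 (6%) |
| 0 | 0.1 | 0.119 (70%) | 0.00 (5%) |
| 0 | 0.2 | 0.236 (99%) | 0.00 (4%) |
| 0 | 0.3 | 0.354 (100%) | 0.00 (6%) |
| 0.1 | 0.3 | 0.454 (100%) | 0.10 (100%) |

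The correlation of 0.71 is deliberately strong. This step shows the mechanism, not a likely size.

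**3. Size under a range of traits, accuracy outcome.** Assumptions: 300 students, 18 items, one inference item per fact, no fact-level effect. The trait stands for what is left after the planned covariates. The reader-level test correlates mean latency with mean accuracy; the within-student test uses the slope after removing student and item means. The ranges cover different amounts of other student variance.

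| Residual trait | Correlation with mean latency | Log-odds per SD | Reader-level rejection |
|---|---|---|---|
| Weak | −0.1 | 0.1–0.2 | about 5–8% |
| Moderate | −0.2 | 0.2 | 9–27% |
| Strong | −0.3 | 0.4 | 38–90% (66–67% at student SD 0.5) |

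The within-student test rejects in 4% to 7% throughout.

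**4. Whether the within-student test is usable.** With a true fact-level effect of 0.15 log-odds per SD of latency and the same layout, its power is 73% to 78% if a single latency has reliability 0.3, and 95% to 96% if it is 0.6. These reliabilities are assumptions.

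**The case against.** **The plan does not commit to one value per student.** A reader might infer that it does, and so chose the wrong level. The documents do not say so. The inference rests on the reader-characteristics label and the total-time index. The plan also defines a per-fact measure, and a model crossing persons with items could carry it. This stands as a limit on the wording. What remains is that no role for the fact-level measure is stated.

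**A between-student question is legitimate.** The Background speaks of readers who lack knowledge or retrieve it slowly, Objective 2 concerns individual differences, and the power statement is about constructs. Aim 1 states no level. A reader might infer that Study 1 asks only which facts get used; the documents do not support that either. The between-student effect should be kept, but labelled as such.

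**Much confounding is already adjusted for.** The model includes working memory, metacognition, reading comprehension, word reading efficiency, background knowledge, availability and grade. It is therefore too strong to say that any unmeasured trait biases the result. The trait must relate to both recall speed and inferencing after those adjustments. General response speed and motivation are candidates not on the list.

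**The simulated sizes rest on assumptions.** They do, and a weak residual trait does almost no harm. The reader-level test simulated is also an unadjusted correlation rather than the planned covariate model, with the trait defined as what the covariates leave.

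**The remedy is not perfectly clean.** Facts recalled wrongly in Phase 1 are presented again until correct, so latency depends on the attempt used and on extra exposures. Centring within student does not remove that.

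**Conclusion.** The point holds as a worthwhile, low-cost improvement. As written, the Study 1 model reads as a between-student comparison, and the latencies collected as a measure of each fact's accessibility are not used, although the outcome is trial-level and the plan asks about inferences from that same knowledge. The direction of the risk is clear. Its size is not: false-positive rates for a fact-level reading run from near nominal to 90%, depending on how strong a trait remains after adjustment and how much other student variance there is. Under every setting tried, the within-student test stayed at 4% to 7%. These results assume 300 students, 18 items and one question per fact, and the documents do not establish that last condition.

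**What to change.** 1. For the inference questions that depend on an identifiable fact or facts, prespecify a question-to-fact key. State how questions that map to several facts are handled, and leave out of this analysis those that map to none.
2. Enter the matched fact's log Verbal-Recall latency as two predictors, the student's mean and the deviation from that mean, and keep item effects in the model.
3. Report the deviation as the fact-level accessibility effect and the student mean as a separate individual-difference effect. State which of them each Study 1 hypothesis refers to.
4. Name the administration and the attempt that supply the latency, and adjust for the number of times each fact was re-presented before criterion.

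**Cost.** A key, one further accessibility predictor, a count of re-presentations and a few sentences in the analysis plan; the latencies are already recorded. Single-fact latencies are noisy, so the within-student slope is attenuated toward zero. A null result there should be read with that in mind. Confounding at the student-by-fact level is reduced by item 4 but not eliminated.

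### Study 1 names item response models for inferencing accuracy but a linear-model procedure to fit them, so the secondary skill-by-accessibility interaction could be tested on either of two scales

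*Combined protocol and SAP*

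**What the plan says.** The Analytic Approach in the Statistical Analysis Plan for Study 1 states that "we will fit mixed effects explanatory item response models to the trial-by-trial inferencing accuracy and speed data using SAS PROC MIXED". The rest of that sentence describes the data structure: "with item-level accuracy and reading speeds cross classified between person and items". Accuracy is therefore analysed item by item. No distribution, link function or second procedure is given for it. The only alternative is to leave accuracy out: "If limited variability exists in the accuracy data, we will only model response time data". The Data Analysis paragraph allows transformations in general terms, but none is named for accuracy.

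The same section sets a secondary hypothesis that accessibility "affects inferencing with that knowledge more so for less skilled than for skilled comprehenders after controlling for knowledge availability". Comprehension skill is kept continuous. The interaction term is not written out, and the scale on which it is tested is not stated.

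Two passages elsewhere bear on the check. Under Phase 2, "Seven questions asked immediately after each text section assess various aspects of text comprehension". Six sections of seven questions make 42 questions of all types, but the number of inference questions is not given. In the Phase 1 Verbal-Recall Task, response times are taken "to provide a measure of accessibility of each knowledge-base item".

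**The concern.** The model and the procedure do not match. PROC MIXED is a reasonable choice for suitably transformed response times. Given item-level accuracy, it fits a linear model for the probability of a correct answer, which is not an item response model. An analyst must depart either from the named model or from the named procedure, and the plan does not say which.

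For a bounded outcome, an interaction on one scale need not exist on another. The choice can therefore decide whether the accuracy data appear to support the secondary hypothesis. Unless the scale is settled before the data are seen, it could be chosen after seeing which one gives the hypothesised result.

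**Working it through.** The plan gives no figure on this point to reproduce. The check asks whether the two routes can give different answers, and how different.

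**1. The two models.** For student i and item j, let S be comprehension skill and A be accessibility coded as retrieval time, so a larger A means slower.
- As the model is named: logit P(correct) = b0 + b1·S + b2·A + b3·S·A + student effect + item effect.
- As the procedure is named: accuracy = b0 + b1·S + b2·A + b3·S·A + student effect + item effect + normal error.

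The secondary hypothesis concerns b3, which is a different quantity in each line. With b1 > 0 and b2 < 0, a positive b3 is the hypothesised direction.

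**2. Why the answers differ.** If b3 = 0 on the logit scale, the probability-scale interaction at accuracy P is b1·b2·P(1-P)(1-2P). It is zero at P = 0.5, in the hypothesised direction above 0.5 and in the opposite direction below. If effects are instead additive in probability (slopes a1 and a2), the logit-scale interaction is a1·a2·(2P-1)/[P²(1-P)²], which has the opposite sign pattern.

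**3. Closed-form example (assumed effects).** Take 70% typical accuracy, so b0 = ln(0.7/0.3) = 0.847. Let skill add 0.5 logits per SD and easier access add 0.4, with no logit interaction.
- Less skilled (-1 SD): accuracy rises from 48.7% to 67.9% as access goes from -1 to +1 SD, a gain of 19.2 points.
- Skilled (+1 SD): accuracy rises from 72.1% to 85.2%, a gain of 13.1 points.
- Difference: 19.2 - 13.1 = 6.1 points. At 50% typical accuracy it is 0.0.

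**4. Simulation.** From the documents: 300 students (the same sentence's 160 per grade over four grades would make 640) and at most 42 questions. Everything else is assumed: 12, 24 or 36 inference items; nominal 5% test (Study 1 states no alpha); skill and retrieval time correlated -0.3; student SD 0.6 and item SD 0.8 for the logit truth; a beta-distributed student probability with precision 12 for the probability truth. Availability is left out for simplicity. There were 3,000 sets per setting. The linear test is least squares on each student's proportion correct, which in balanced data equals the mixed-model test for student-level predictors. The logit test is an overdispersed binomial logit. Entries are the percentage of sets in which an interaction is found.

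| Accuracy | Logit-additive truth (0.5/-0.3 logits per SD): linear test | Probability-additive truth (0.08/-0.05 per SD): logit test |
|---|---|---|
| 50% | 2.6-3.3 | 4.4-5.2 |
| 60% | 7.8-10.0 | 6.5-8.6 |
| 70% | 22.9-33.2 | 21.2-29.9 |

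The test on the same scale as the truth stays at 3.7-5.5% (logit) and 3.1-5.4% (linear).

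- A second simulation with the same main effects gave the linear test 4-5%, about 9% and 19-27%. Combining the two gives 3-5%, 8-10% and 19-33%. A simplified version gave 7% at 60% and 16-23% at 70%.
- Direction: from 60% accuracy up, at least 96% of the linear rejections favour the hypothesis. Under the probability truth, logit rejections favour it in at most 1.4% of sets.
- Below 50%: the linear test rejects in 7.7-11.0% at 40% and 20.2-32.7% at 30%, almost all against the hypothesis.
- Smaller effects (0.3/-0.2): linear about 4%, 5% and 7-10% at 50%, 60% and 70%.
- A maximum-likelihood random-intercept logit with a likelihood-ratio test (400 sets, 12/24 items) at 70%: linear 20.3%/30.5%, logit 3.7%/3.5%.
- Accessibility entered per item, half its variance within student, at 70%: linear 14.7%/20.5%, logit 8.5%/4.8%.

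**5. Cost of requiring agreement on both scales.** Logit interaction of size 0.15, power of logit alone against agreement on both scales, 12/36 items:
- Hypothesised direction, 70% accuracy: 0.72/0.89 against 0.72/0.89.
- Opposite direction, 70%: 0.77/0.92 against 0.26/0.35.
- Hypothesised direction, 30%: 0.75/0.92 against 0.24/0.35.

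A repeat of the last two gave 0.68/0.88 against 0.26/0.35, and 0.69/0.87 against 0.22/0.35.

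**The case against.** The strongest reply is that the plan does point to a scale. An item response model conventionally means a logit or probit link, so this is close to a wrong software name. That is partly right, and it is why the fix follows the named model. But the named procedure points the other way and no link is written. Routes exist that call PROC MIXED repeatedly on linearised data, but the plan does not mention one.

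A reader might infer that the linear model's rejections are false positives. The documents and the arithmetic do not support that. When effects are additive in logits, the probability-scale interaction is real (6.1 points in the example), and the linear test correctly rejects a different null hypothesis. Nor is logit shown to be the true scale; the mirror-image result rules out that argument.

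A reader might also take the Scientific Background's report that accessible knowledge is twice as likely to be used as a ceiling on accuracy. It does not bound accuracy here: that study used easier texts and left out less skilled readers, and the ratio need not carry over.

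The reach is narrow, which stands. One secondary hypothesis is affected, for accuracy only; response time also addresses it, and accuracy may be dropped altogether.

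**Conclusion.** The concern holds in a limited form. The named procedure does not fit the named model for accuracy, and nothing else in the document repairs this. The choice between them can change the answer to the secondary skill-by-accessibility question. It makes little difference near 50% accuracy or with small effects, a modest difference at 60%, and a large one at 70% with the larger assumed effects. These rates rest on assumed effects, item counts and accuracy levels; they show direction and possible size and are not a forecast.

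A reader might infer that the Study 1 analysis as a whole is unsound. It is not: PROC MIXED suits transformed response times, and the Aim 1 main-effect question does not turn on scale in this way. A reader might likewise see a contradiction in the crossed structure alongside "treating grouping variable for people such as grade and items as fixed factors". That, the item scoring rule and the undefined threshold for limited variability are missing detail, not separate errors, and in balanced data the linear test of student-level predictors is the same with items fixed or random. The point should be fixed, but it is not fatal.

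**What to change.** Fit accuracy with a generalized mixed model that matches the item response model already named, for example in PROC GLIMMIX: binomial with a logit link, or ordinal if partial credit is scored. The Phase 2 text leaves scoring open ("When a student answers a question incorrectly or incompletely, the research assistant will use a nonspecific prompt to elicit a fuller response"), so the choice between the two should be stated. Keep PROC MIXED for transformed response time.

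Write out the interaction term. State in advance that for accuracy it is tested on the logit scale and also reported on the probability scale, and that it will be described as scale-dependent if the two disagree. Do not make agreement on both scales a condition for significance. That costs no power only for an interaction in the hypothesised direction with accuracy above 50%, and can otherwise cost more than half of it.

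The cost is revised SAP wording, a different SAS procedure for accuracy, longer run time and one extra reported contrast. No new data are needed.
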